4.3.3 Presentation of results

The safety analysis set will be used for the immunogenicity evaluation. For tables by analysis visit, analysis visits during the observation or follow-up phase will not be shown (but will be included in listings). Only analysis visits for which an assessment of the applicable parameter is scheduled per SoA will be included.

Frequency tabulations (number and percentages of participants) will be provided with ADA negative/positive/unevaluable samples per analysis visit and by ADA against efgartigimod participant classification.

Frequency tabulations (number and percentages of participants) for efgartigimod will be provided in 1 table for:

- ADA evaluable and unevaluable participants
- ADA study baseline sample status

	Statistical Analysis Plan	
ARGX-113-2010	Final analysis	Final 1.0 of 29APR2025

- ADA participant classification
- incidence and prevalence of ADA

The above frequency tabulations will be repeated for the NAb assay.

In addition, a frequency tabulation (number and percentages of participants) will be provided for:

- NAb against efgartigimod positive participants within efgartigimod ADA participants classification (treatment-unaffected ADA, treatment-induced ADA, treatment-boosted ADA, ADA negative and ADA unevaluable).

ADA titer values against efgartigimod titer values will be summarized by means of descriptive statistics by ADA participant classification at each analysis visit.

All available data on ADA and NAb against efgartigimod will be listed for the ROL analysis set, also showing the ADA and NAb sample status and participant classification.

	Statistical Analysis Plan	
ARGX-113-2010	Final analysis	Final 1.0 of 29APR2025

5. SAFETY ANALYSES

5.1 ADVERSE EVENTS

5.1.1 Available data

Adverse events will be coded into system organ classes (SOC) and preferred terms (PT) using the latest version of the MedDRA dictionary available at the time of the database lock of ARGX-113-2009.

For each AE, start and stop date/times will be collected as well as severity, a seriousness flag, relationship to IMP, prednisone (or equivalent) and procedures, action taken towards IMP and prednisone (or equivalent) and outcome.

The grade (severity) of AEs will be assessed by the investigator according to the National Cancer Institute (NCI) Common Terminology Criteria for Adverse Events (CTCAE) version 5.0.

5.1.2 Derivation rules

TEAEs are defined as AEs with onset on or after the first administration of IMP in ARGX-113-2010 up to and including 60 days after the last IMP administration before the event. Figure 2 depicts an example of the assessment of TEAEs for a participant with two treatment periods.

Figure 2: Treatment-emergent adverse events

D1-D40	D41-D199		D200-D260	D261-D337		FU
IMP	No IMP		IMP	No IMP		No IMP
TEAE: D1-D40	TEAE: D40+60 days	Non-TEAE: D101-199	TEAE: D200-D260	TEAE: D260+60 days	Non-TEAE: >D320	Non-TEAE

IMP = investigational medicinal product; TEAE = treatment-emergent AE

AEs will be considered treatment-emergent based on their start date(time). If the AE start date(time) is incomplete or missing, the AE will be considered treatment-emergent unless the available parts of the AE start or stop date(time) provide evidence that the event did not occur in the interval during which an event is considered treatment-emergent. No imputation of missing/incomplete dates will be done.

Based on their start date/time, AEs will be allocated to the phase in which they started. Each AE will therefore be reported in only one phase. Phases are defined in section 2.2.1. In case the AE start date/time is incomplete or missing, and the AE could consequently be allocated to more than one phase, a worst-case allocation will be done and the AE will be allocated to the treatment phase, unless the available parts of the AE start and stop date/time provide evidence for allocating to the observation or follow-up phase.

A death case is defined as an AE with outcome ‘fatal’.

An AE for which the study drug was discontinued is defined as an AE with action taken ‘drug withdrawn’.

	Statistical Analysis Plan	
ARGX-113-2010	Final analysis	Final 1.0 of 29APR2025

AEs with missing relatedness to treatment, prednisone (or equivalent) or procedures will be considered as treatment-related, prednisone-related or procedure-related respectively.

AEs with missing seriousness will be considered as serious AEs.

Within the efgartigimod program, infections are considered AESIs and are defined as events with a PT that falls under the MedDRA SOC ‘Infections and infestations’.

IRRs are defined as all AEs with a MedDRA PT that is listed in either:

- Hypersensitivity standardized MedDRA query (SMQ) (broad selection)
- Anaphylactic reaction (SMQ) (broad selection)
- Extravasation events (injections, infusions and implants) (SMQ) (broad selection), excluding implants

AND occurs within 48 hours of an injection, or within 2 days if the AE start time is not available. If the AE start date is incomplete, the AE will be considered as an IRR, unless the available parts of the AE start date provide evidence it did not occur within 48 hours of an injection.

ISRs are defined as AEs with MedDRA PT in the MedDRA high level term of “Injection site reactions”, regardless of the time of onset relative to an administration.

AE onset and day since last administration will be calculated as follows when start date is fully known:

- AE onset day in the study (vs baseline visit) =
 - AE start date \geq date of baseline visit: AE start date – date of baseline visit + 1 day
 - AE start date < date of baseline visit: AE start date – date of baseline visit
- Day since last administration: AE start date - date of last IMP before AE start date

AE duration will be calculated as follows when start and stop date are fully known:

- AE duration (days) =
 - AE end date – AE start date + 1 day
 - End date of the last phase – AE start date + 1 day (when the AE start date is fully known but the AE is not resolved at the end of the study). In this case the duration will be presented as “>x days” in listings.

Event rates per 100 participant years of follow-up (PYFU) will be calculated as $100 \times \frac{\text{number of events}}{\text{PYFU}}$, with:

- PYFU overall (in years) will be calculated as [the sum over all participants of the study duration calculated as (last phase end date - first phase start date + 1)]/365.25
- PYFU for TEAEs (in years) will be calculated as the sum over all participants of the follow-up time during which an event is considered treatment-emergent divided by 365.25.

	Statistical Analysis Plan	
ARGX-113-2010	Final analysis	Final 1.0 of 29APR2025

5.1.3 *Presentation of results*

The SAF analysis set will be used for the reporting of AEs, unless mentioned otherwise. Tables will present the combined treatment and follow-up phase and will present TEAEs only, unless mentioned otherwise.

An overview table will show the number and percentage of participants with at least one event, the number of events and the event rates per 100 PYFU for the following:

- TEAEs
- Treatment-related TEAEs
- Serious TEAEs
- Serious treatment-related TEAEs
- Serious prednisone-related TEAEs
- Grade ≥ 3 TEAEs
- Treatment-related grade ≥ 3 TEAEs
- TEAEs related to prednisone (or equivalent)
- TEAEs related to study procedures
- TEAEs for which the IMP was discontinued
- TEAEs for which the IMP was interrupted
- TEAEs of special interest *
- Treatment-related TEAEs of special interest *
- TEIRRs *
- Serious TEIRRs *
- TEISRs *
- Fatal TEAEs *

This overview table will be repeated for:

- Overall AEs: all AEs during the study, also including non-TEAEs. This table will be based on the ROL analysis set.
- Treatment-emergent ISR events (TEISRs), excluding the event categories marked with "*" in the above list.

Summary tables by MedDRA SOC and PT will include the number and percentage of participants with at least one event, the number of events and the event rates per 100 PYFU. Each AE record in the clinical database is considered as a distinct adverse event and is counted as such. Summary tables by SOC and PT will be sorted alphabetically.

These tables will be provided for:

- TEAEs
- Overall AEs (based on the ROL analysis set)
- Treatment-related TEAEs
- Serious TEAEs

	Statistical Analysis Plan	
ARGX-113-2010	Final analysis	Final 1.0 of 29APR2025

- Serious treatment-related TEAEs
- Serious prednisone-related TEAEs
- Grade ≥ 3 TEAEs
- Treatment-related Grade ≥ 3 TEAEs
- TEAEs related to prednisone (or equivalent)
- TEAEs related to study procedures
- TEAEs for which the IMP was discontinued
- TEAEs of special interest
- Treatment-related TEAEs of special interest
- TEIRRs
- Serious TEIRRs
- TEISRs
- Fatal TEAEs
- Common TEAEs (PT occurring in at least 5% of the Total Efgartigimod PH20 SC treatment arm; the cut-off is applied after rounding to the nearest integer. System organ class will be presented if any preferred term within it is selected.)

All AEs, including non-TEAEs will be listed for the ROL analysis set (but excluding AEs that started during ARGX-113-2009). Separate listings will be prepared for SAEs, fatal AEs, TEAEs leading to IMP discontinuation (in the SAF analysis set) and AESIs. A listing showing all coding information will be prepared as well.

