1.1 STUDY OBJECTIVES AND ENDPOINTS

Table 1: Objectives and endpoints

Objectives	Endpoints
Primary	
To assess the long-term safety and tolerability of treatment with efgartigimod PH20 SC in participants with BP	
 • Incidence and severity of treatment-emergent AEs, SAEs, and AESIs • Rate of treatment discontinuation because of safety concerns
Secondary	
To assess the long-term efficacy and durability of response with efgartigimod PH20 SC treatment in participants with BP	
 • Proportions of participants achieving^a: 
 ○ CR while off OCS for ≥ 8 weeks ○ CR or PR while off OCS for ≥ 8 weeks ○ CR while on minimal OCS therapy for ≥ 8 weeks. (Minimal OCS therapy is defined as ≤ 0.10 mg/kg/day of prednisone [or an equivalent dose of another OCS]) ○ CR while off both OCS and efgartigimod PH20 SC for ≥ 8 weeks^b ○ CR or PR while off both OCS and efgartigimod PH20 SC for ≥ 8 weeks^b • Duration of sustained remission • Proportion of participants who relapse • Time to relapse • Incidence and severity of relapse • BPDAI activity scores, IGA-BP scores, and itch NRS over time • Rate of treatment failure

	Statistical Analysis Plan	
ARGX-113-2010	Final analysis	Final 1.0 of 29APR2025

Additional secondary	
To evaluate the impact of efgartigimod PH20 SC treatment in reducing long-term glucocorticoid-associated toxicity in participants with BP	
 GTI-related scores, including the GTI-AIS, GTI-CWS, and GTI-SL over time
To evaluate the impact of efgartigimod PH20 SC treatment on QoL in participants with BP	
 EQ-5D-5L, DLQI, and ABQOL scores over time
To evaluate the PD and immunogenicity of efgartigimod PH20 SC in participants with BP	
 Percent change from baseline over time for anti-BP180 and anti-BP230 antibody levels Incidence and prevalence of ADA against efgartigimod (serum levels)
Exploratory	
[REDACTED]	
 [REDACTED]

- ^a These endpoint criteria can only be met when participants are off rescue therapy.
- ^b The endpoint applies only to participants who have stopped receiving efgartigimod PH20 SC before protocol amendment 2 is effective.

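### AEs ongoing from ARGX-113-2009 that turn serious or fatal, or stop IMP, in the extension are in no TEAE table and may be in no AE listing

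*SAP*

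**What the plan says.** The two primary endpoints (SAP 1.1) are "Incidence and severity of treatment-emergent AEs, SAEs, and AESIs" and "Rate of treatment discontinuation because of safety concerns".

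SAP 5.1.2 gives the AE rules:
- Treatment emergence: "TEAEs are defined as AEs with onset on or after the first administration of IMP in ARGX-113-2010 up to and including 60 days after". The 60 days are counted from the most recent dose given ahead of the event. Only the start date is used. Later changes in grade, seriousness, action taken or outcome play no part.
- Phase: "Based on their start date/time, AEs will be allocated to the phase in which they started". Under SAP 2.2.1, Table 2, the earliest phase opens on the date of the extension's baseline visit.
- Deaths: "A death case is defined as an AE with outcome" 'fatal'.

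SAP 5.1.3 gives the outputs. AE tables show TEAEs on the safety set unless stated otherwise. The stated exceptions are an overall overview and an overall SOC/PT table on the rollover set (14.3.1.2 and 14.3.1.4), which also take in non-TEAEs. The AE listing covers the rollover set "but excluding AEs that started during ARGX-113-2009". The next sentence adds: "Separate listings will be prepared for SAEs, fatal AEs, TEAEs leading to IMP discontinuation (in the SAF analysis set) and AESIs".

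Separately, SAP 3.1 tabulates treatment and study discontinuation by reason from the termination pages (Tables 14.1.1.4 and 14.1.1.5). Protocol 9.3.1 commits to summarizing AEs that lead to death or to discontinuation of efgartigimod PH20 SC, and sets no condition on when they began.

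**The concern.** The extension's baseline is the same day as the parent study's end-of-treatment visit (protocol 8.1), so there is no gap in which open AEs could resolve. Protocol 5.5 admits participants whose IMP was interrupted at that visit. Exclusion criterion 3 still admits some who permanently stopped parent IMP for a related AE, if benefit/risk is judged positive. Protocol 2.3.1 describes an older population with comorbidities. AEs open at rollover are therefore foreseeable.

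If such an AE becomes serious or fatal after extension dosing starts, its start date keeps it out of the outputs that serve the first primary endpoint. A death could appear as a disposition reason with no event, grade or relatedness beside it. The omission runs in one direction, because it can only reduce the counts of serious, fatal and IMP-withdrawal AEs.

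**Working it through.** No sample size, power or alpha figure bears on this point. The check is whether the TEAE rule is read correctly, and where events of different onset then land.

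**Step 1: reproduce the SAP's own example.** In SAP 5.1.2, Figure 2, IMP is given on D1–D40 and D200–D260. The window runs from first dose to last preceding dose + 60 days: 40 + 60 = D100 and 260 + 60 = D320. This gives TEAE windows D1–D100 and D200–D320, which agree with the figure.

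**Step 2: trace three onsets.** Baseline is day 1, and the last dose is taken as D337, so the window closes at 337 + 60 = D397. In each case suppose that the AE later turns serious or fatal, or stops IMP.

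| | Began in ARGX-113-2009 (day −20; first dose D1) | Began in extension before first dose (D30; first dose D60) | Began on IMP (D100; first dose D1) |
|---|---|---|---|
| TEAE by rule | No (−20 < 1) | No (30 < 60) | Yes (1 ≤ 100 ≤ 397) |
| TEAE tables (e.g. 14.3.1.6, 14.3.1.13, 14.3.1.20) | Absent | Absent | Present |
| Overall AE tables 14.3.1.2, 14.3.1.4 (ROL) | Not stated; belongs to no extension phase | Present | Present |
| AE, SAE, fatal and AESI listings (16.2.7.1, .2, .3, .5; ROL) | Excluded from 16.2.7.1, and from the others if they are its subsets | Present | Present |
| Listing 16.2.7.4 (TEAEs leading to IMP discontinuation) | Absent | Absent | Present |
| Table 14.1.1.4, if IMP stops | Counted | Counted | Counted |

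Only the first column can end with no AE output at all.

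**Step 3: set the AE rule beside the SAP's rule for abnormalities.** The SAP's Definition of Terms counts a laboratory, vital-sign or ECG abnormality or toxicity as treatment-emergent if it is new or has worsened since study baseline, with the same 60-day limit. Its example is a hemoglobin of grade 1 at baseline that reaches grade 2 later. An AE of grade 2 at rollover that ends as grade 5 is not treatment-emergent under 5.1.2. The primary endpoint thus has the narrower rule.

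**Step 4: set it beside the protocol.** Protocol 9.3.1 has no onset condition for AEs leading to death or discontinuation. The dedicated outputs are the fatal-TEAE table, the fatal-AE listing, and the TEAE-only IMP-discontinuation table and listing. None is keyed to date of death or to when IMP was withdrawn.

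**The case against.** **Collection rules may already solve it.** Protocol 10.3.1 collects exacerbations of preexisting conditions as AEs, and 10.3.3 makes death grade 5 and treats grades 4 and 5 as always serious. SAP 5.1.3 counts each record as a separate event. If the site opens a new record dated in the extension, the event is a TEAE. This stands as a mitigation but does not close the gap. Nothing in either document requires a new record when an open AE becomes fatal or serious or leads to withdrawal, and the eCRF completion guidance is not available here.

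**The exclusion may be narrower than it looks.** It is a parenthesis on the general AE listing, and the sentence on SAE and fatal listings does not repeat it. SAP 5.1.2 also has an onset-day formula for AEs that start before baseline, so such records may be in the database. This stands too, which is why the claim is that these events may be absent from the listings.

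**Eligibility limits the cases.** Exclusion criterion 1 and the infection measure in protocol 2.3.1, Table 3 screen out some serious open conditions. They make the scenario rarer, not impossible.

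**Attribution by onset is defensible.** Some of these AEs began on parent-study placebo. That argues for a flag, not for leaving the event out.

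**Stronger readings a reader might infer.** One is that all AEs before the first extension dose vanish from fatal and withdrawal outputs. They do not: those with onset in the extension are in the overall AE tables and in the SAE, fatal and AESI listings. Another is that safety discontinuations are lost from the second primary endpoint. They are not: Table 14.1.1.4 counts IMP discontinuations by reason from the termination page, and the endpoint wording is not restricted to TEAEs.

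**Conclusion.** The point holds for AEs that began in ARGX-113-2009 and were still open at rollover. If they worsen, become serious, turn fatal or stop IMP in the extension, they are in no TEAE table. Unless a new record is opened, they may be in no AE listing, and their place in the overall AE tables is not stated. This conflicts with protocol 9.3.1 and departs from the SAP's own worsening rule for abnormalities. For AEs that start in the extension before the first dose, the gap is limited to TEAE-labelled outputs such as Table 14.3.1.13 and Listing 16.2.7.4.

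The size cannot be computed, because the documents contain no AE or death counts. A reader might want a figure such as a fatal-AE rate of 3% in place of 4%. That needs assumed counts (100 dosed, 4 deaths, 1 of them from a parent-onset AE) and is only an illustration. What can be said is that each such event lowers the affected count by one. The study is descriptive, so no test or decision rule changes.

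The conclusion assumes that sites may update the open record and not start a new one. For the SAE and fatal listings, it also assumes that they follow the general AE listing's exclusion.

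**What to change.** 1. In SAP 5.1.2, also count as treatment-emergent an earlier-onset AE that increases in grade, becomes serious or turns fatal after the first extension dose and within the 60-day window.
2. Tabulate and list all on-study deaths on the rollover set by date of death, whatever the AE onset.
3. In SAP 5.1.3, exempt from the listing exclusion parent-onset AEs that become serious or fatal, or lead to IMP withdrawal, in the extension. Flag them 'onset in ARGX-113-2009', so that pooled analyses with the parent study do not count them twice. State whether the overall AE tables include open parent-onset AEs.
4. Base the table and listing of AEs leading to IMP discontinuation on action taken 'drug withdrawn' in the extension, regardless of onset, and reconcile them with Table 14.1.1.4. Name the output that reports the second primary endpoint, since the SAP does not.

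The cost is SAP wording and flag derivations in ADAE. SAP 5.1.1 mentions no date for a change in grade or seriousness, so item 1 may need the status at rollover compared with the final status, or a rule that worsening opens a new record. A few events are added and the safety counts become slightly less favourable. Some of the added AEs will have begun on parent-study placebo, and the flag lets a reader identify them.

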5.2 CLINICAL LABORATORY EVALUATION

5.2.1 Available data

Per protocol, the following safety laboratory parameters are expected:

Laboratory test	Parameters		
Hematology	RBC count platelet count hemoglobin hematocrit	RBC indices: MCV MCH	WBC count with differential: neutrophils lymphocytes monocytes basophils eosinophils
Biochemistry	ALT AST ALP albumin bilirubin (total and direct) BUN sodium	calcium creatinine CRP GGT glucose HbA1c potassium	total protein Lipid panel: total cholesterol HDL LDL (measured, not calculated) triglycerides

	Statistical Analysis Plan	
ARGX-113-2010	Final analysis	Final 1.0 of 29APR2025

Laboratory test	Parameters
Routine urinalysis	Specific gravity pH, glucose, protein, blood, ketones, bilirubin, urobilinogen, nitrite, leukocyte esterase Microscopic examination (if blood or protein is abnormal)
Specialty laboratory tests	INR

For each laboratory record, laboratory test, test result in standardized unit, and sample date(time) are collected. Normal ranges are available as provided by the laboratory.

5.2.2 Derivation rules

The following abnormality categories will be defined:

- Low: value < lower limit of normal range
- Normal: lower limit of normal range ≤ value ≤ upper limit of normal range
- High: value > upper limit of normal range

Notes:

- Abnormalities will be derived for hematology and biochemistry parameters for which no toxicity grading is defined.
- Classification will be performed in standardized units, using nonimputed values and limits.
- For the worst-case analysis visit, as defined in section 2.2.5, an additional category low + high is defined if there are both low and high postbaseline values

Toxicity grades will be computed according to the NCI CTCAE toxicity grading list (version 5.0). The implementation of these toxicity grades for analysis is presented in appendix 9.2. Only the parameters described in appendix 9.2 will be computed, according to the declared limits for each grade.

